## **Statistical Considerations**

**Statistical Analyses:** To maintain blinding, the statistician who is otherwise not directly involved in the study will conduct the analysis based on the intention-to-treat principle. Below, we have outlined the specific analysis plan for assessing each of the three aims of interest of this study. As part of the analyses of the three aims, we plan to account for potential confounding. We will assess for statistically significant differences in baseline study characteristics, including age, sex, race, history of suicide attempts, mental health diagnosis, marital status, employment, recent life stressors, service history, High Risk for Suicide List status, and Suicide Prevention Pathway status between study arms using *t*-tests for continuous measures and chi-squared tests

for dichotomous variables. We will report these results using 95% confidence intervals (CI) and *P*-values. We will define statistical significance as a *P*-value < 0.05. If we identify any variables for which there are significant differences across study arms, we will control for these confounders in the analysis of the aims.

**Specific Aim 1:** The primary aim of the study is to determine whether PEACE plus standard psychiatric hospital discharge care reduces suicidal ideation after psychiatric hospitalization compared to standard psychiatric hospital discharge care, alone. Based on available evidence, we hypothesize that the intervention plus standard psychiatric hospital discharge care will lead to a significant reduction in suicidal ideation after psychiatric hospitalization. We believe that the effect of the intervention on suicidal ideation will be the greatest at the three-month assessment because the greatest intensity of follow-up care provided through the intervention occurs within the first three months after discharge. In order to assess whether the effect of the intervention is maintained after the intervention is discontinued, we will reassess patients at six months (i.e., three months after the intervention has been discontinued). This length of follow-up is feasible within the scope of this mentored award period and more than 50% of suicide attempts occur within six months after discharge. We will generate descriptive summary statistics (e.g., means and standard errors, medians) and graphical displays for the BSS total scores at baseline (assessment 1) and at assessments 2, 3, and 4. Aligned with evidence from the literature, we will use a hurdle model to analyze our primary outcome. First, we will use logistic regression whereby we will treat the measure as a dichotomous outcome with zero versus nonzero values (i.e. presence or absence of any suicidal ideation). Second, we will look at the degree of suicidal ideation by using a zero-truncated over-dispersed negative binomial regression for the distribution of nonzero values. The BSS scale is a 21-item scale. The first five items are intended to evaluate for the presence of any suicidal ideation. These items together get at the complex construct of suicidal ideation including passive and active suicidal ideation. As described in the literature, all 5 initial items on the BSS are used to define the presence or absence of suicidal ideation (i.e. “zero” on all of the first five questions defines “no suicidal ideation present”). If suicidal ideation is present, then additional items (i.e. items 6-19) are used to evaluate the severity of suicidal ideation.

We will calculate 95% CI and *P*-values and will define a *P*-value of < 0.05 to be statistically significant. We will use the maximum likelihood ratio to account for any missing data.

**Specific Aim 2:** The secondary aim of our study is to determine the mechanism by which PEACE exerts its anti-suicidal effect on patients after psychiatric hospital discharge. Based on available evidence, we hypothesize that the intervention plus standard psychiatric hospital discharge care exerts an anti-suicidal effect on patients after psychiatric hospitalization by improving social connectedness and engagement in care after discharge. We will assess this aim by performing the following analyses: First, we will perform an analysis to demonstrate whether there are greater improvements in social connectedness and engagement in care over time in patients assigned to the intervention versus control condition at one, three, and six months after discharge. For continuous variables measuring patient engagement, we will generate descriptive summary statistics (e.g., means and standard errors, medians) and graphical displays for each measure at baseline (assessment 1) and at assessments 2, 3, and 4. Second, using structural equation modeling, we will calculate mean differences in scores for each of our continuous measures at the one-, three-, and six-month assessment periods, as well as the associated 95% confidence intervals and *P*-values. For the categorical measure of patient engagement, we will use chi-squared tests to compare the proportion of patients adhering to their discharge plan between the two study arms at one-month after discharge. Third, we will assess whether social connectedness and patient engagement mediate the effect of the intervention on suicidal ideation, as measured by total BSS scores. In order to conduct this analysis, we will use structural equation modeling. We will use the maximum likelihood to account for any missing data. We will calculate the associated 95% CIs and *P*-values and will define a *P*-value of 0.05 to be statistically significant.

**Specific Aim 3:** We plan to conduct an exploratory analysis on the number of suicide attempts (fatal and non-fatal) that occur after discharge in the intervention plus standard psychiatric hospitalization discharge care arm compared to standard psychiatric hospital discharge care, alone. While suicide deaths and suicide attempts are important clinical endpoints, this single-site trial will not be powered to detect a statistically significant effect between study arms. Furthermore, because we assume that few events will be observed in either arm, we plan to summarize our findings by providing basic descriptive statistics regarding the number of events in each arm at one-, three-, and six-month follow-ups. In the event that there are a sufficient number of suicide attempt events to perform statistical analysis, we will use a log-rank statistic to test for statistically significant differences in the proportion of suicide attempts between arms. We will use the Kaplan-Meier method to plot and compare survival curves for each arm. Specifically, we will calculate the time from the baseline assessment (assessment 1) to first suicide attempt after discharge for each study arm. Patients who are lost to follow-up or do not attempt suicide will be censored during the analysis. We will calculate hazard ratios using the Cox proportional hazards model. This approach will also enable us to adjust for baseline differences between study arms, if necessary. We plan on using these data to inform a future trial that is powered to detect an effect.

**Proposed Secondary Analysis:** Within the intervention group, we will conduct a secondary analysis of engagement with the mHealth app to assist further in the interpretation of our findings. Specifically, we are interested in learning about the degree to which patients assigned to PEACE interacted with app and whether differences in the degree of engagement with the app are associated with changes in social connectedness and suicidal ideation. First, we will generate descriptive summary statistics (e.g., means and standard errors, medians) and graphical displays for app engagement at one and three-month follow-up. Second, we will use generalized linear modeling to evaluate the relationship between app engagement and the primary outcome, suicidal ideation, and the secondary outcome, social connectedness.

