AES = App Engagement Scale; BHS = Beck Hopelessness Scale; BSS = Beck Scale for Suicidal Ideation; CSSR-S = Columbia Suicide Severity Rating Scale; INQ-15 = Interpersonal Needs Questionnaire-15; M = months; MINI = MINI International Neuropsychiatric Interview; MSPSS: Multidimensional Scale of Perceived Social Support; N/A = Not applicable; SRCS: The Suicide-Related Coping Scale; \*Time is described in minutes

**Baseline Characteristics:** We will collect socio-demographic data from patient report and the electronic medical record such as age, sex, marital status and service history (e.g., branch, era, combat exposure). We will also collect diagnostic information using the MINI International Neuropsychiatric Interview (MINI), which has been validated against the Structured Clinical Interview for Diagnostic and Statistical Manual of Mental Disorders (DSM). The MINI is a short, structured diagnostic interview that, on average, takes about 15 minutes to administer. We will inquire about any history of suicide attempts using the validated Columbia Suicide Severity Rating-Scale (C-SSRS). The C-SSRS includes a 7-item subscale that assesses for actual and interrupted suicide attempts.

**Primary Outcome (Suicidal Ideation):** The primary outcome will be assessed using the Beck Scale for Suicidal Ideation (BSS). Patients will be asked about their current suicidal ideation (i.e., past week) at assessments 1 as well as at assessments 2, 3, and 4. The BSS is a self-reported questionnaire that assesses severity of suicidal ideation. The BSS measures attitudes, behaviors, and plans to die by suicide. Each item on the BSS is scored on a scale from 0 to 2 and the first 19 of the 21 items are used to calculate a total score ranging from 0 – 38. The BSS has high reliability and is a valid measure of suicidal ideation. There is also evidence that the BSS is measurement invariant across time. The BSS is widely used in clinical trials, is sensitive to clinical change, and unlike most other measures of suicidal ideation, higher scores on the BSS are associated with death by suicide. While there is no established BSS cutoff score to classify suicide risk as

high, low, or none, there is evidence that higher scores on the BSS correspond to more severe suicidal ideation. There is evidence that an improvement of five points or more on the total BSS scores may be clinically relevant.

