### Sample Size:

Based on a pilot RCT of the VA BIC Program in 19 patients discharged from the WRJ VAMC inpatient mental health unit (manuscript currently under review), we found that the intervention had an estimated effect size of 0.5 (Cohen's  $d_s$ ) on the BSS. We see the 0.5 as a medium sized effect and consistent with effects of other psychosocial interventions. We have reason to believe that this effect size may be even higher in our trial where we will be

enhancing the intervention with the addition of the mHealth app. We used these pilot data to re-calculate the required sample size for this proposed study. In doing so, we used a formula for

Table 3. Sample size estimates

Power	Alpha	$p$	n	Effect Size	Size of Effect	Intervention	Control	Intervention	Control
0.8	0.05	0.5	4	0.3	Small	109	109	120	120
0.8	0.05	0.5	4	0.5	Medium	40	40	46	46
0.8	0.05	0.5	4	0.6	Medium	27	27	30	30
0.8	0.05	0.5	4	0.8	Large	16	16	18	18

*p = correlation of repeated measures; n = 4 timepoints; N=number*

*\*Size of effect are based on criteria described in Laken D 2013.*

estimating sample sizes for longitudinal designs with repeated measures as proposed by Hedeker et al (1999). We assumed that the correlation of repeated measures ( $p$ ) was 0.5 based on findings from our pilot data. Furthermore, we assumed that there were four assessment points and that the data followed a normal distribution. We made this latter assumption because our pilot data followed a normal distribution according to the Shapiro-Wilk test for normalcy. We also are assuming that the data that we collect in this proposed trial will follow a normal distribution because the data will be drawn from the same population (and the same setting) as our pilot work. As shown in **Table 3**, based on the aforementioned calculations, a sample size of 80 (40 per arm) will achieve an 80% power to detect an effect size of 0.5 (Cohen's  $d$ ) or greater between arms across the study timepoints with a significance level of 5%. In our pilot study, there were no patients who dropped out, but

two patients had missing data at one or three-month follow-up. Conservatively, we assumed that in the proposed trial that there could be a drop out as high as 10%. This means that we will need to recruit for this proposed trial a sample size of **92** (46 per arm).

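### Covariates are chosen by baseline significance tests, and the role of baseline BSS in the primary hurdle model is left unspecified

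*Combined protocol and SAP*

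**What the plan says.** Under Statistical Considerations, the Statistical Analyses paragraph compares baseline characteristics between arms with t-tests and chi-squared tests at P < 0.05, and then says: "If we identify any variables for which there are significant differences across study arms, we will control for these confounders". The rule covers the analysis of all three aims. Eleven characteristics are named, from age to Suicide Prevention Pathway status. Baseline BSS is not one of them, although the list is worded as open.

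Specific Aim 1 sets out a hurdle model: a logistic part for any ideation, then a "zero-truncated over-dispersed negative binomial regression for the distribution of nonzero values". No covariates are listed for either part, and baseline BSS is mentioned only for descriptive summaries and graphs. The missing-data sentence reads "We will use the maximum likelihood ratio to account for any missing data". Specific Aim 3 echoes the covariate rule for the Cox model: "This approach will also enable us to adjust for baseline differences between study arms, if necessary".

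The Outcome Measures section and its Table 2 schedule the BSS at baseline and at one, three and six months; "the first 19 of the 21 items are used to calculate a total score". In the Sample Size section the correlation of repeated measures "was 0.5 based on findings from our pilot data", and "we assumed that there were four assessment points and that the data followed a normal distribution".

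**The concern.** After proper randomisation, a significant baseline difference is a chance event. Its P-value says nothing about whether the variable predicts suicidal ideation at follow-up. A rule that selects on that P-value makes the primary model depend on the draw and can pass over the variable most likely to matter. If a selected variable does predict outcome, adding it also changes the odds ratio being estimated, so the target of the analysis would not be fixed in advance.

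Baseline BSS is the obvious prognostic covariate, and the plan's own correlation assumption implies that it is useful. If it is left out or only screened, precision is lost.

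A secondary issue concerns the zero-truncated part. It is fitted only to patients with nonzero follow-up scores, a subset formed after randomisation. The arms may differ at baseline within that subset. The planned test compares all randomised patients and cannot detect this.

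**Working it through.** **1. The plan's own figure.** For the mean of four equally correlated visits, n per arm = 2(1.960 + 0.842)² × [(1 + 3ρ)/4] / d². With ρ = 0.5 and d = 0.5 this is 2 × 7.849 × 0.625 / 0.25 = 39.24, so 40, as stated in Table 3. The sample size is not in dispute here.

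**2. How often the rule selects something.** With 11 independent tests at 0.05, 1 − 0.95¹¹ = 0.431. If service history is split into the three examples given under Baseline Characteristics, there are 13 tests and 1 − 0.95¹³ = 0.487. Correlated variables lower both figures, and the plan does not fix the number of tests. Any single variable, including baseline BSS if it is screened, is selected about 5% of the time.

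**3. Power in the hurdle model (illustrative).** Evaluable n = 46 × 0.9 = 41 per arm, one follow-up visit. Baseline B is standard normal. The latent follow-up value is Y = ρB + √(1 − ρ²)e − 0.5 × arm. The score is zero below a cut-off c that sets the control-arm zero share; otherwise it is 7(Y − c) rounded up and capped at 38. Likelihood-ratio tests at 0.05, 10,000 runs per setting. Screened means that B is added only if its between-arm t-test has P < 0.05. Entries are unadjusted / screened / always adjusted, in %.

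| Control zeros | ρ | Logistic part | Count part |
|---|---|---|---|
| 20% | 0.5 | 39/39/46 | 25/25/35 |
| 35% | 0.3 | 46/46/46 | 17/17/20 |
| 35% | 0.5 | 46/46/50 | 17/17/24 |
| 35% | 0.7 | 47/47/59 | 17/18/37 |
| 50% | 0.5 | 45/45/50 | 13/13/17 |

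The zero shares, the latent-normal form, the score scale, the constant treatment effect and the values of ρ other than 0.5 are assumptions. Both d and ρ act on the latent scale: at 35% zeros and ρ = 0.5 the generated scores have d of about 0.44 and a baseline correlation of about 0.46. The logistic results were checked with separate code; the count results were not.

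**4. Type I error.** With no effect (35% zeros, ρ = 0.5 and 0.7), the screened rule rejects in 5.0% and 4.3% of runs (logistic) and 4.6% and 4.4% (count). The adjusted logistic test rejects in 6.0% and 5.5%, against 5.4% and 5.0% unadjusted. Up to about 0.6 point of the logistic gain is therefore small-sample test size.

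**5. A normal-theory variant of the Sample Size framework.** Take the mean of the three follow-up visits. The variance factor is (1 + 2ρ)/3 = 0.667 unadjusted, and 0.667 − ρ² = 0.417 adjusted for baseline. Power is Φ(0.5/√(2f/n) − 1.96). At n = 40 this is Φ(2.739 − 1.96) = 0.78 and Φ(3.464 − 1.96) = 0.93. Simulation at 41 per arm gives 78/80/93% for unadjusted / screened / adjusted. This is not the power of the hurdle model.

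**6. Selection within the nonzero subset (35% zeros, ρ = 0.3, 0.5, 0.7).** Under a constant effect, treated patients with nonzero scores exceed their control counterparts at baseline by about 0.09, 0.15 and 0.21 SD. If the latent benefit is 0.5 + 0.25 × baseline SD, the excess is −0.13, −0.04 and +0.07. With 0.5 + 0.5 × baseline SD it is −0.35, −0.29 and −0.16. The sign is not determined.

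Under the constant effect, adjustment moves the count ratio from 0.80 to 0.77 at ρ = 0.5. The mean difference moves from −1.36 to −1.62, against a built-in −3.5 (7 × 0.5) in patients who would be nonzero in either arm. That closes 0.26/2.14, about 12% of the gap. At ρ = 0.7 it moves from −1.38 to −1.98, closing 0.60/2.12, about 28%.

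**The case against.** The strongest reply is that the text is open rather than wrong about baseline BSS. The list of baseline variables is not exhaustive, four assessment points are counted in the sample size, and the hypotheses speak of greater reductions, all of which fit a longitudinal model that uses baseline. That stands as far as it goes: the accurate charge is that the role of baseline BSS is unspecified. A reader might infer that the plan excludes it, and the documents do not support that. Nor do they supply a baseline term. If baseline were an outcome row, the logistic part would have almost no zeros there, since the safety section expects high ideation in all patients at entry. The significance-test rule itself is explicit, and an open list does not rescue it, because screening recovers almost nothing.

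The second reply is that the gain is modest and rests on assumptions. This also stands. At ρ = 0.5 the logistic gain is 4 to 7 points, and at ρ = 0.3 it is nil. The pilot BSS data were reported as consistent with normality, so the zero shares are uncertain. One visit was simulated although three follow-ups are planned.

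Third, a reader might infer that the zero-truncated comparison is biased against PEACE. That holds under a constant effect but can reverse if benefit varies with severity, and the documents do not say which applies.

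**Conclusion.** The point holds as one of pre-specification and precision, and it should be fixed before analysis. The textual finding is firm: covariates are chosen by chance imbalance, and baseline BSS has no stated analytic role.

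The magnitudes are illustrative. For the logistic part at 35% zeros, pre-specified adjustment adds about 0, 4 and 12 points of power at latent correlations of 0.3, 0.5 and 0.7. Count-part gains at ρ = 0.5 are of similar size (4 to 10 points across the zero shares tried), but they partly reflect a changed contrast rather than added precision. The 78/80/93% figures belong to normal theory with three visits and should not be read as hurdle-model power. Nor should the single-visit figures be read as the power of the trial.

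A reader might infer that the rule inflates type I error; the null simulations do not show this, and it is not claimed. The subset issue in the count part is secondary. Its direction is unknown, and baseline adjustment addresses it only in part.

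**What to change.** - Delete the significance-test rule for choosing covariates, and bring the matching Aim 3 sentence into line.
- Pre-specify the baseline BSS total (19 items) as a covariate in both hurdle parts, whatever the baseline comparisons show, with assessments 2 to 4 as the outcomes.
- State that the odds ratio and the count ratio are conditional on baseline BSS. State also that the count part compares a subset formed after randomisation, and that baseline adjustment reduces but does not remove any resulting imbalance.
- In Aim 2, adjust for the baseline value of each scale that has one (INQ-15, MSPSS, SRCS, BHS).
- Keep adjustment for observed imbalances as a sensitivity analysis only.

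The cost is one extra parameter in each hurdle part and a little SAP wording. Baseline BSS is already collected, and no patients are added.

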My long-term goal is to develop a career as an independent clinical researcher with a focus on developing, testing, and improving interventions to prevent suicide in Veterans. To achieve this goal, my overall objective for this application is two-fold: First, I aim to obtain the skills needed to build my professional career and conduct clinical research in suicide prevention by learning how to: (1) design and adapt clinical interventions; (2) design, conduct, and manage clinical trials; and (3) perform research in patients at high risk for suicide. Second, I aim to study the efficacy of a novel, two-component intervention called PEACE. My central hypothesis is that PEACE will lead to greater reductions in suicidal ideation after psychiatric hospitalization, compared to standard care alone. I hypothesize that PEACE exerts its effect by improving social connectedness and engagement in care. The rationale for this proposal is that the results from this single-site trial will advance my knowledge in designing effective strategies to prevent suicide, which I will use to develop a future merit award proposal. To attain the overall objectives, the following specific aims will be pursued:

- 1. To identify the effect of PEACE on suicidal ideation after psychiatric hospitalization, compared to standard care alone.** My hypothesis is that PEACE will lead to greater reductions in suicidal ideation at one, three, and six months after hospitalization, compared to standard care.
- 2. To identify the effect of PEACE on social connectedness and engagement in care after psychiatric hospitalization, compared to standard care alone.** My hypothesis is that PEACE will lead to greater

improvements in social connectedness and engagement in care at one, three, and six months after hospitalization, compared to standard care.

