### **Overview of Intervention and RCT Design:**

As shown below in **Figure 2**, to test the aforementioned hypotheses, we propose to conduct a single-site, assessor-blinded RCT at the WRJ VAMC comparing PEACE plus standard psychiatric hospital discharge care to standard psychiatric hospital discharge care alone. The trial will enroll patients 18 years and older who are being discharged from the WRJ VAMC inpatient mental health unit (called Ground East, GE). The primary aim is to determine whether PEACE reduces suicidal ideation at one, three, and six months after psychiatric hospitalization. The secondary aim is to determine the mechanism by which PEACE exerts its anti-suicidal effect after hospitalization. An exploratory aim includes describing the number of suicide attempts after discharge.

**Baseline Assessment and Randomization:** Prior to the start of study enrollment, allocation cards will be prepared using a fixed-block randomization scheme. These cards will be put into sealed, opaque, numbered envelopes. The box of envelopes will be stored in a locked cabinet in the study coordinator's locked office.

The study team member will meet with each eligible patient in a private room on GE at the WRJ VAMC around the time of discharge. The study team member will obtain informed consent from the patient and then administer the baseline assessments, which are described under the outcome measures (see below). The baseline visit will take approximately 90 minutes to complete. Study staff will also contact the support person the patient selected to obtain consent from this person.

After obtaining consent and completing the baseline assessments, the study coordinator will take the next numbered envelope from the box (described above) and open the envelope to determine the patient's assignment. In the event that the patient has been assigned to the intervention, the study coordinator will notify the intervention staff in order that the intervention staff can initiate the intervention. Otherwise, the patient will be informed that they have been assigned to usual care.

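### Aim 1 has two model parts and three visits but no named deciding test, while Table 3 sizes the trial for a single time-averaged contrast

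*Combined protocol and SAP*

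**What the plan says.** Specific Aims/Purpose states the Aim 1 hypothesis as "PEACE will lead to greater reductions in suicidal ideation at one, three, and six months after hospitalization, compared to standard care". The Overview of Intervention and RCT Design repeats the three visits: "The primary aim is to determine whether PEACE reduces suicidal ideation at one, three, and six months after psychiatric hospitalization".

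Statistical Considerations, Specific Aim 1, sets out a hurdle model in two parts:

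- any ideation: "First, we will use logistic regression whereby we will treat the measure as a dichotomous outcome with zero versus nonzero values";
- severity: "Second, we will look at the degree of suicidal ideation by using a zero-truncated over-dispersed negative binomial regression for the distribution of nonzero values".

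The criterion is a P-value below 0.05. On timing, the section says "We believe that the effect of the intervention on suicidal ideation will be the greatest at the three-month assessment" and explains that the six-month visit shows whether the effect lasts. A likelihood sentence deals with missing data. No random effect, GEE or covariance structure is named for Aim 1.

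On covariates, the Statistical Analyses paragraph tests baseline characteristics for differences between arms and, for those that differ significantly, says "we will control for these confounders in the analysis of the aims".

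On the outcome, the Primary Outcome paragraph says "the first 19 of the 21 items are used to calculate a total score". Specific Aim 1 uses items 1 to 5 for presence of ideation and says that "additional items (i.e. items 6-19) are used to evaluate the severity of suicidal ideation".

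Sample Size uses a repeated-measures formula for normal data with four timepoints and correlation 0.5. It reports 40 per arm for 80% power at d = 0.5, and 46 per arm after allowing for 10% dropout.

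**The concern.** A hurdle model yields two arm effects, and three visits can turn these into six. The plan does not say which of them, or which combination, answers the primary question. The deciding result would therefore be settled at the analysis stage, and the operating characteristics depend on what is then chosen.

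Three features of the same text add to this.

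- **Within-patient structure.** Each patient contributes up to three follow-up scores, and the model has no stated term for that. The longitudinal sample-size formula suggests that a longitudinal model was intended, but even a valid longitudinal hurdle model leaves two arm effects.
- **Selection in the severity part.** It compares only patients with nonzero scores at follow-up. That group is formed after randomisation and may itself be changed by the intervention, so this part should not decide the trial alone.
- **Baseline BSS.** It is adjusted for only if the arms happen to differ significantly on it, although it is likely to be a strong predictor of follow-up BSS.

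**Working it through.** **Inputs.** Sample Size and Table 3: power 80%, alpha 5%, correlation rho = 0.5, m = 4 timepoints, d = 0.5, 40 evaluable and 46 recruited per arm, 10% dropout. With 46 × 0.9 = 41.4, I use 41 per arm. Assumptions of mine: two-sided testing (Table 3 reproduces that way), the same correlation of 0.5 between all visits including baseline, and complete data.

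**1. Reproduce Table 3.** For a time-averaged difference with equal correlations,

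n per arm = 2(1.960 + 0.842)² × [1 + (m − 1)rho] / (m d²) = 2 × 7.849 × 2.5 / (4d²).

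| d | computed | printed |
|---|---|---|
| 0.3 | 109.0 | 109 |
| 0.5 | 39.2 | 40 |
| 0.6 | 27.3 | 27 |
| 0.8 | 15.3 | 16 |

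All four rows match, though rounding is not uniform. At d = 0.5 a single visit would need 2 × 7.849 / 0.25 = 62.8, so 63 per arm. Averaging only the three follow-up visits gives 2 × 7.849 × 2 / (3 × 0.25) = 41.9. Table 3 is therefore one averaged contrast, tested once.

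**2. False positives under rules the plan leaves open.**

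- Either of two independent parts counts: 1 − 0.95² = 9.75%.
- Any part at any visit counts, all six tests independent: 1 − 0.95⁶ = 26.5%. With the three visits correlated within each part and the parts independent (simulated normal test statistics, 4,000,000 draws): about 23.5% at correlation 0.5 and 16% at 0.9.

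**3. Power if all three visits must be significant on mean BSS** (d = 0.5 at each visit, 41 per arm).

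- Unadjusted: each visit's test statistic has mean 0.5 / √(2/41) = 2.264, correlation 0.5 between visits. The joint probability that all three exceed 1.960 is about 37%.
- Baseline-adjusted: residual variance is 1 − 0.5² = 0.75, so the mean is 0.5 / √(2 × 0.75/41) = 2.614. The correlation becomes (0.5 − 0.25)/0.75 = 0.333, and the joint probability is about 49%.

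**4. Power of single deciding contrasts** (41 per arm). The standard error is √(2v/41). For the three-visit average, v = 2/3 unadjusted and 2/3 − 0.25 = 0.417 adjusted. For one visit, v = 1 and 0.75.

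| True effect at 1, 3, 6 months | Averaged, unadjusted | Averaged, adjusted | 3 months, unadjusted | 3 months, adjusted |
|---|---|---|---|---|
| 0.5, 0.5, 0.5 | 79% | 94% | 62% | 74% |
| 0.25, 0.5, 0.25 | – | 65% | – | 74% |
| 0, 0.5, 0 | – | 22% | – | 74% |

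As a worked entry, the averaged adjusted contrast with equal effects is 0.5 / √(2 × 0.417/41) = 3.507, and Φ(3.507 − 1.960) = 0.94.

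The power of the hurdle parts themselves cannot be derived from the documents. They give no share of zero scores, dispersion, odds ratio or rate ratio.

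**The case against.** The strongest reply is that the intention can be read from the whole document. A longitudinal sample-size formula implies a longitudinal model, three months is where the effect is expected to peak, and nobody wrote that any one of six results would count. Much of this is fair. A reader might infer that the trial will run at a 23.5% error rate, or that visits will be pooled as if independent. The documents support neither inference. They state no such rule, and the sample-size section points away from naive pooling. Nor do they require significance at all three visits. What the reply does not supply is a deciding test: the three-month remark is an expectation, and the six-month remark concerns maintenance.

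A reader might also infer that the BSS is defined in two contradictory ways. That goes too far. The 19-item total and the split into items 1–5 and 6–19 can be read together as a presence screen followed by the total score. What stands is an ambiguity that one sentence would remove.

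Similarly, baseline BSS is not excluded from adjustment. The covariate list is introduced as illustrative, and BSS is measured at baseline. What is missing is adjustment regardless of observed imbalance.

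Finally, the hurdle model is a defensible choice for scores with many zeros, and replacing it with a linear mixed model is partly preference. The need to name the deciding contrast holds under either model.

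**Conclusion.** The concern holds, and the plan should be changed before unblinding. One primary hypothesis has two model parts, three visits, one unqualified P-value threshold and no stated within-patient structure, while the trial was sized for a single averaged contrast that the analysis section never defines.

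The finding that no deciding test is named comes from the text and needs no assumption. The sizes are conditional. False positives of 9.75% to 26.5% apply only if more than one result may count as success. Power of 37% or 49% applies only under an all-visits rule on mean BSS. The power figures rest on d = 0.5 at every visit unless stated otherwise, correlation 0.5, normal theory and complete data; missing visits were not examined.

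**What to change.** Before unblinding, name one primary test at two-sided 0.05 that uses all randomised patients, state how repeated visits are modelled, and always adjust for baseline BSS.

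- **Closest to Table 3:** the arm difference in mean BSS, zeros included, averaged over one, three and six months. It can come from a repeated-measures mixed model (arm, visit, arm-by-visit, baseline BSS, baseline-by-visit, unstructured within-patient covariance, small-sample degrees of freedom). It can equally be computed from the hurdle model with patient-clustered variance and a small-sample correction. It is not identical to Table 3, which counts baseline as a fourth timepoint.
- **Also acceptable:** a named three-month contrast, or one 2-df joint test of both hurdle parts.

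Report the separate hurdle parts and the remaining visits as secondary. Add one sentence defining the outcome: zero means items 1–5 all score 0, and the count is the 19-item total. A sum of items 6–19 alone could be zero and could not enter a zero-truncated model.

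The cost is SAP wording and a standard model. A significant result on one part or one visit would no longer be enough, and averaging dilutes an effect concentrated at three months. If the sponsor expects mainly a three-month effect, the three-month contrast is the better single test. If it expects a similar effect at all visits, the averaged contrast is.
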